5.0 OBJECTIVES

5.1 Primary Objectives

The **overarching aim of this study** is to implement this OUD-CDS in a large multi-site clinic-randomized controlled trial to evaluate its impact on practice process measures and patient outcomes in at least 30 primary care clinics across three healthcare systems.

Specific Aims:

Aim 1. To implement OUD CDS in primary care settings and assess its impact on process measures related to diagnosis of patients at high risk for OUD, as well as prescription of naloxone for patients at high risk for or diagnosed with OUD.

H1.1: Patients previously undiagnosed with OUD but identified as high risk by the OUD-CDS at an index visit will be more likely to receive an OUD diagnosis (in the problem list or as an ICD-10 visit code) in intervention clinics than in UC clinics within 30 days post-index.

H1.2: Patients previously diagnosed with OUD or identified as high risk by the OUD-CDS at an index visit will be more likely to have naloxone rescue kits ordered in the intervention clinics than in the UC clinics within 30 days post-index.

Aim 2. To assess the impact of OUD-CDS on important patient outcomes of initiation and maintenance of Medications for Opioid Use Disorder (MOUD) in patients identified as having OUD or being at high risk for OUD.

H2.1: Patients identified as having OUD or as being at high-risk for OUD by the OUD-CDS at an index visit will be more likely to have MOUD orders or referral for OUD treatment within 30 days post-index in intervention clinics than in UC clinics.

H2.2: Patients identified as having OUD or as being at high-risk for OUD by the OUD-CDS at an index visit will have significantly more days covered by a MOUD prescription at 90 days post-index in intervention clinics than in UC clinics.

Aim 3. To assess the long-term impact of OUD CDS on important patient outcomes in patients with OUD or identified as high risk for OUD.

H3.1: Patients with OUD or identified as high-risk for OUD by the OUD-CDS who are cared for in intervention clinics will have significantly fewer post-index ED visits during the observation period (i.e., the period between each patient's index date and last observation) compared to patients cared for in UC clinics.

H3.2: Patients with OUD or identified as high-risk for OUD by the OUD-CDS who are cared for in intervention clinics will have significantly fewer post-index hospitalizations during the observation period compared to patients cared for in UC clinics.

Aim 4. To describe and quantify costs of OUD-CDS implementation and maintenance and the short-term cost impacts of the OUD-CDS.

H4.1: After controlling for demographics, baseline clinical status and prior costs of care, patients with OUD or identified as high risk for OUD by the OUD-CDS will have lower healthcare costs in intervention compared to UC clinics during the observation period (i.e., savings from lower ED visits and hospitalizations will outweigh increased costs of OUD treatment and naloxone rescue kits and OUD-CDS implementation and maintenance).

Aim 5. To use mixed quantitative and qualitative methods to identify, describe and quantify barriers and facilitators to implementation of the OUD-CDS so that it can be adapted to maximize its use and effectiveness.

5.2 Secondary Objective(s)

Among patients with OUD or identified as high-risk for OUD, we will assess secondary outcomes, which include whether those who are cared for in intervention clinics have lower rates of all-cause death and of fatal and non-fatal opioid overdoses during the intervention period compared to similar patients in UC clinics during the observation period.

Treatment effectiveness may vary as a function of contextual as well as patient factors. In secondary analyses, care system indicators (Site 1, Site 2, Site 3) and clinic characteristics (e.g., proportion of primary care patients eligible for OUD-CDS, proportion of clinic patients with government-sponsored insurance) may be added to the primary model as main effects and in interaction with the treatment group indicator to assess treatment heterogeneity due to contextual factors. Patient characteristics (e.g., race, ethnicity, age, estimated neighborhood income and education, documented heroin vs. oral opioid use) may be similarly added to the primary model to assess treatment heterogeneity due to patient factors.

The OUD-CDS tool is hypothesized to improve process measures of appropriate care for patients at high risk for or diagnosed with OUD by alerting PCPs to the risk of OUD and presenting them with tools and treatment advice that support the delivery of recommended care. For each PCP who practices at an intervention clinic, we will assess the extent to which engagement with the OUD-CDS (e.g., opening or printing OUD-CDS recommendations, use of embedded screening tools) is associated with patient outcomes. Via surveys, we will also assess PCP ratings of confidence in treating OUD and their satisfaction with the OUD-CDS.

5.3 Exploratory Objective(s)

In exploratory analyses, we may assess whether (a) PCPs in intervention clinics who are non-waivered at go-live dates are more likely to become buprenorphine-waivered than PCPs in UC clinics during the intervention period; (b) waived PCPs in intervention clinics are more likely to prescribe buprenorphine than PCPs in UC clinics during the intervention period; (c) whether PCPs in intervention clinics who are non-waivered at go-live dates are reportedly more likely to prescribe buprenorphine should a waiver no longer be required than PCPs in UC clinics measured prior to go-live dates and at 9 months following go-live dates; (d) if we have adequate data, potentially via health plan or Surescripts data, whether adherence/persistence to methadone, buprenorphine, XR-NTX or therapy for patients with OUD differs for patients in intervention vs. UC clinics during the observation period; and (e) PCPs in intervention clinics are more likely to screen their patients for mental health conditions and infectious diseases than PCPs in UC clinics during the intervention period.

6.0 STUDY DESIGN

6.1 Overview of Study Design

We propose to implement OUD-CDS in a large multi-site clinic randomized pragmatic trial to evaluate its impact on practice process measures and patient outcomes. We also aim to prepare for scalability by evaluating facilitators and barriers to implementation, determining the costs of implementation and maintenance, and assessing cost effectiveness of the OUD-CDS. The trial will include three large geographically dispersed care systems that constitute a racially, ethnically and socioeconomically diverse patient population. At least 30 clinics will be randomized to receive the OUD-CDS intervention or UC. Randomization will be stratified by care system, with key pre-randomization clinic measures balanced across treatment arms. Randomization in each healthcare system will be approximately 1:1. In intervention clinics, the OUD-CDS will identify patients who are at high risk for or previously diagnosed with OUD; use data stored in the EHR for these patients to assemble treatment recommendations tailored to the current needs of each patient; display these recommendations via the OUD-CDS user interface; and store analytic data from all targeted visits. In UC clinics, the OUD-CDS will run invisibly in the background to identify high-risk and OUD diagnosed patients, assemble treatment recommendations and store analytic data from all targeted visits. The targeted visits for each study-eligible patient in all randomized clinics will be the index visit, the first visit at which the OUD-CDS identifies that the patient is eligible, and all post-index visits through the end of the observation period. Patients who are identified as eligible during the accrual period and meet all inclusion and exclusion criteria will be considered for inclusion in the primary outcome analyses. Patient outcomes will be derived from the data elements stored by the OUD-CDS at all targeted visits. To the extent it is available, EHR data from the year prior to the index visit through the end of the observation period will be included in primary and secondary analyses. Process outcomes at or following the index visit (Aims 1 and 2), and clinical outcomes following the index visit through the end of the observation period (Aim 3), will be compared between patients cared for in intervention and UC clinics to assess the effectiveness of OUD-CDS.

6.2 Duration of Study and Visit Schedule

Primary care clinics will be randomized within each health care system to receive or not receive access to the OUD-CDS. Once OUD-CDS is implemented in each health care system, its algorithms automatically identify eligible patients in all randomized intervention and UC clinics, independent of any PCP actions. PCPs in clinics with CDS access are anticipated to have access to the OUD-CDS intervention through May 2024, depending on factors such as healthcare system leader preference. In UC clinics, the OUD-CDS will run silently in the background over the same time period, collecting data without displaying. There is no study-determined visit schedule; rather, patient visits will be jointly determined by the patient and PCP. We plan to stop collecting outcome data in October 2023 at all sites. We anticipate patient observation periods of 19 to 31 months from date of index visit, depending on the site. Having the OUD-CDS run from implementation through the end of the observation period in all randomized clinics in each health care system ensures that identical methods are used to identify study-eligible patients and track patterns of OUD-related care so that we may quantify the impact of the OUD-CDS on OUD identification and care.

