- Varies by system
- OUD-CDS implementation date through a predetermined time at which the Wizard interfaces will be turned off in the intervention clinics

Accrual Period

- Varies by system
- OUD-CDS implementation date through a predetermined time at which no more people will be included in the analytic sample

Index Date

- Varies by patient
- First visit at which the OUD-CDS identifies that the patient is study eligible

Observation Period

- Varies by patient
- Index visit date through a predetermined time at which outcome data will no longer be accumulated

H1.2: Patients previously diagnosed with OUD or identified as high risk by the OUD-CDS at an index visit will be more likely to have naloxone rescue kits ordered in the intervention clinics than in the UC clinics within 30 days post-index.

Aim 2. To assess the impact of OUD-CDS on important patient outcomes of initiation and maintenance of Medications for Opioid Use Disorder (MOUD) in patients identified as having OUD or being at high risk for OUD.

H2.1: Patients identified as having OUD or as being at high-risk for OUD by the OUD-CDS at an index visit will be more likely to have MOUD orders or referral for OUD treatment within 30 days post-index in intervention clinics than in UC clinics.

H2.2: Patients identified as having OUD or as being at high-risk for OUD by the OUD-CDS at an index visit will have significantly more days covered by a MOUD prescription at 90 days post-index in intervention clinics than in UC clinics.

Aim 3. To assess the long-term impact of OUD CDS on important patient outcomes in patients with OUD or identified as high risk for OUD.

H3.1: Patients with OUD or identified as high-risk for OUD by the OUD-CDS who are cared for in intervention clinics will have significantly fewer post-index emergency department (ED) visits during the observation period (i.e., the period between each patient's index date and last observation) compared to patients cared for in UC clinics.

H3.2: Patients with OUD or identified as high-risk for OUD by the OUD-CDS who are cared for in intervention clinics will have significantly fewer post-index hospitalizations during the observation period compared to patients cared for in UC clinics.

Aim 4. To describe and quantify costs of OUD-CDS implementation and maintenance and the short-term cost impacts of the OUD-CDS.

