2.4 Treatment/Assessment/Intervention and Duration

The OUD-CDS provides clinical guidance to PCPs in the screening, diagnosis and treatment of OUD, along with common comorbid conditions, and will display for patients with OUD or at high risk for OUD in intervention primary care clinics during each site's intervention period (see timeline). PCPs are also able to access the OUD-CDS in EPIC for patient encounters for which it did not display (e.g., new patient visits). Patient follow-up time from the date of index visit is estimated to range from 18 to 31 months.

The OUD-CDS will be tested and evaluated prior to implementation, in the early implementation phase, and during the maintenance phase at each site by a combination of qualitative data collection, monitoring of use rates and PCP surveys at all time points.

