8.2 PCPs and Clinic Staff

To be eligible for inclusion in this study, a PCP must be a family physician, general internist, or adult-care non-obstetric nurse practitioner (NP) or physician assistant (PA) working at a study-eligible primary care clinic. PCPs who are and who are not buprenorphine-waivered are study eligible. PCPs in the intervention clinics will be encouraged but not required to use the OUD-CDS with eligible patients, so that the decision to use or not use OUD-CDS at a given clinical encounter is up the PCP at each clinical encounter. All PCPs will be asked to consent to and complete pre- and post-implementation surveys and may receive modest compensation for completing these surveys. In the intervention phase, PCPs who are high-, moderate- and low/non-users of the OUD-CDS will be invited to participate in interviews. Clinic staff associated with invited PCPs (e.g., rooming staff, nurses) will also be invited to participate. PCPs and staff who are asked to participate in interviews will be consented for those interviews and may receive modest compensation. Exclusive of consenting PCPs for interviews and surveys, we will request a waiver of written informed consent for PCPs from the IRB for the intervention because (a) the OUD-CDS is based on current national standards of OUD identification and management and does not make any treatment recommendations that are not accepted as community standard of care, and (b) consenting PCPs would compromise the external validity of the study by introducing selection effects. Measures to protect the privacy of PCPs participating in this study are described further

below. The OUD-CDS may also be turned on for non-PCP clinicians affiliated with intervention clinics, such as pharmacy staff, and a similar waiver of written informed consent will be requested by the IRB. These non-PCP clinicians may also be invited to participate in surveys or interviews.

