8.3 Patients

To be eligible for inclusion in the study, a patient must meet all the following eligibility criteria: (a) be aged 18-75 years, inclusive, at the time of an index visit; (b) have been diagnosed with OUD, currently prescribed MOUD, or identified by study algorithms as being at high risk of OUD. There are no exclusions for pregnancy, lactation, or mental health or behavioral health issues. However, patients who meet the following criteria at the time of their index visit will be excluded and not be exposed to the OUD-CDS intervention: (a) those receiving active parenteral chemotherapy within the last year, (b) those with stage 4 or equivalent cancer diagnosis, (c) those enrolled in hospice care or palliative care programs. All women and members of racial or ethnic minority groups and their subpopulations who meet the above eligibility criteria and do not meet exclusion criteria will be included in accordance with the National Institutes of Health (NIH) Policy on Inclusion of Women and Minorities as Participants in Research Involving Human Subjects. A sample of patients with diagnoses of OUD and/or identified as being at high risk for OUD and/or referred by a PCP will be invited to participate in interviews and surveys. Patients who are asked to complete surveys or participate in interviews will be consented and will receive modest compensation. Beyond survey and interview participation, we will request and anticipate receiving a waiver of written informed consent from the governing IRB for patient participation because the study is minimal or less than minimal risk compared to the risk associated with any primary care encounter, and because the study could not be conducted if written informed consent were required to be obtained in the context of busy community-based primary care clinic environments. We have requested and received such waivers of written informed consent for patients in several similar prior studies. Note that patients who have requested non-participation in research studies at any of the participating care delivery systems will be excluded from all analyses.

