Definition of High Risk: Algorithms determine when a patient is identified as being at high risk for OUD or opioid overdose, and, in intervention clinics, this will trigger a best practice alert to be displayed for a particular patient at a particular clinic encounter. These algorithms, like all of the OUD-CDS algorithms, are housed on a web platform that interacts with the EHR to pull data elements to run risk equations and determine patient eligibility. We anticipate that how the algorithms will identify patients at high risk of OUD or opioid overdose will evolve over time as our ability to predict risk improves. In early phases of this study, we may use EHR data elements such as long-acting opioid prescriptions, concomitant benzodiazepine and opioid prescriptions, mental health diagnoses, alcohol and substance use diagnoses and previous opioid overdose diagnoses to identify patients at increased risk of OUD or opioid overdose.[31] We may also use, in care systems where this is available, a risk equation developed and validated by EPIC that estimates a patient's risk of OUD or opioid overdose within the next year. As the study progresses, we anticipate incorporating additional calculators for high risk into our algorithms. In work funded by NIDA (1R01DA047724-01, PI [name]), we are developing risk calculators for suicide in people with OUD, as well as risk calculators for unintentional opioid overdoses, in a population of nearly 8 million patients across 7 care systems. Variables in these risk models will include prescription opioid use, prescription opioid use reduction, prescription opioid discontinuation, opioid-related overdose, OUD and/or MOUD prescription, and illicit opioid use.

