12.0 TRAINING REQUIREMENTS

12.1 Overall

A comprehensive Training Plan will be developed to incorporate general training, study-specific training, and mechanisms for competency assessment. The Investigative Team is responsible for the development of a comprehensive Training Plan, instructional material, and delivery of the training (e.g., via self-study, online, webcast, or teleconference), with the team comprised of the Lead Node, Clinical Coordinating Center (CCC), Data and Statistics Center (DSC), as well as other participating nodes and subject matter experts, as applicable. PCPs who are in primary care clinics randomized to receive the OUD-CDS will be trained on how to diagnosis and manage OUD in primary care, use of the OUD-CDS, and the importance of using the Feedback Tab to let the study team know of any issues or questions. Traditionally, we have completed such trainings at in-person lunch meetings with clinic personnel, but will also consider other training modalities, such as web-based trainings or teleconferences, depending on the standard training practices at partner sites and clinic leadership preference.

Study staff will be trained as specified in the Study Training Plan and are required to complete institutionally required training per their research site, IRB(s), and authorities with regulatory oversight. Training will include Human Subject Protection (HSP) and Good Clinical Practice (GCP), as well as protocol-specific training. Tracking of training completion for individual staff as prescribed for assigned study role(s) will be documented, endorsed by the site Principal Investigator and the Lead Node, and audited by the CCC. As changes occur in the prescribed training, the Training Plan and training documentation tracking forms will be amended to reflect these adjustments.

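### Patients enter the cohort after go-live, partly through clinician-recorded diagnoses and prescriptions, so treatment arm can affect who enters and when even though the same algorithm runs in both arms

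*Combined protocol and SAP*

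**What the plan says.** Section 6.2 states that once the tool is live, "its algorithms automatically identify eligible patients in all randomized intervention and UC clinics, independent of any PCP actions". It goes on to say that running the same software in every clinic means study-eligible patients are found by identical methods.

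Section 8.3 requires a patient to "have been diagnosed with OUD, currently prescribed MOUD, or identified by study algorithms as being at high risk of OUD". For the high-risk route, early versions of the algorithm may use "long-acting opioid prescriptions, concomitant benzodiazepine and opioid prescriptions, mental health diagnoses, alcohol and substance use diagnoses and previous opioid overdose diagnoses".

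Section 2.1 defines the index date as the "First visit at which the OUD-CDS identifies that the patient is study eligible". Section 6.1 adds: "Patients who are identified as eligible during the accrual period and meet all inclusion and exclusion criteria will be considered for inclusion". Section 7.2 gives accrual periods of 7 to 18 months by system, extendable by 3 months. Section 10.2 attributes each patient to the arm of the index-visit clinic.

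Three provisions apply to the intervention arm only:
- Section 12.1: PCPs in clinics randomized to the tool "will be trained on how to diagnosis and manage OUD in primary care".
- Section 2.4: "PCPs are also able to access the OUD-CDS in EPIC for patient encounters for which it did not display (e.g., new patient visits". Section 10.2 makes the interface operative only in intervention locations.
- Section 8.2: "The OUD-CDS may also be turned on for non-PCP clinicians affiliated with intervention clinics, such as pharmacy staff".

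**The concern.** Eligibility is determined after randomization from EHR fields, and PCPs write some of those fields. If one arm is better trained to diagnose OUD, and can open the tool for patients it has not flagged, some patients may enter that arm because they have just been diagnosed or treated. Their counterparts in usual care would enter later by another route, or not at all.

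Such entrants are likely to have naloxone orders, MOUD orders or referrals, and covered days soon after index. That pushes H1.2, H2.1 and H2.2 towards benefit without any true effect. It also changes the case mix for Aims 3 and 4, in a direction the documents do not settle. H1.1 is restricted to previously undiagnosed high-risk patients. It would not gain these entrants, but it could lose from the intervention denominator patients who were diagnosed before being flagged. Analysis by index clinic does not repair this, because the denominators themselves would differ.

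**Working it through.** **Step 1. Which mechanisms can act before index?**

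| Mechanism | Can it change first entry? | Basis |
|---|---|---|
| Alert displayed for a flagged or diagnosed patient | No. The patient is already eligible and the index visit is fixed | 2.1, 2.4, 10.1 |
| Training in diagnosing and managing OUD | Yes. It can act on any patient of an intervention PCP | 12.1 |
| Tool opened where it did not display, followed by diagnosis or MOUD | Yes. The patient can qualify at the next visit | 2.4, 8.3 |
| Manually opened call on a patient who already qualifies | Possibly. It could set an earlier index, and no rule excludes it | 2.1, 10.2 |
| Tool turned on for non-PCP staff | Possibly. The text says only that this may happen | 8.2 |

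Manually opening the tool does not make an ineligible patient eligible; the algorithm must still find a qualifying record. The supplied text describes no rule limiting index visits to automatic calls, no comparison of entry route by arm, and no analysis limited to patients who qualified before go-live.

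**Step 2. The plan's own benchmark (Section 13.2.2.1).** Inputs: 30 clinics, 50 patients each, ICC 0.03, usual-care rate 5%, two-sided alpha 0.05, power 0.80.
- Design effect = 1 + 49 × 0.03 = 2.47.
- Effective n per arm = 15 × 50 / 2.47 = 303.6.
- With t on 28 df (2.048 + 0.855 = 2.903), solve (p − 0.05) / √{[0.05 × 0.95 + p(1 − p)] / 303.6} = 2.903. This gives p = 11.42%, against 11.35% (odds ratio 2.43) in the plan.

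The plan's figure is reproduced closely and is not in dispute.

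**Step 3. Size of the bias under assumed inputs.** None of these inputs except the usual-care rates (from the plan's power grid) is in the documents. Let r be the usual-care rate, f the extra entrants relative to the common cohort, and e their outcome probability. With no true effect, the intervention rate is p = (r + f·e) / (1 + f).

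Example: r = 0.05, f = 0.03, e = 0.5 gives (0.05 + 0.015) / 1.03 = 6.31%. The odds ratio is (0.0631 / 0.9369) / (0.05 / 0.95) = 1.28.

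**Step 4. Rejection probability with no true effect.** This uses a noncentral t on 28 df with noncentrality (p − r) / SE, where SE uses the effective n. Section 14.3.1 expects more than 10,000 patients, or about 10,000 / 30 = 333 per clinic. At ICC 0.03 the effective n per arm is 15 × 333 / (1 + 332 × 0.03) = 456. At ICC 0.01 it is 15 × 333 / (1 + 332 × 0.01) = 1,156.

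Usual-care rate 5%:

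| f | e | Rate | OR | 30×50, ICC 0.03 | 30×333, ICC 0.03 | 30×333, ICC 0.01 |
|---|---|---|---|---|---|---|
| 2% | 50% | 5.9% | 1.19 | 7.5% | 8.8% | 14.8% |
| 3% | 50% | 6.3% | 1.28 | 10.4% | 13.1% | 26.1% |
| 5% | 50% | 7.1% | 1.46 | 18.8% | 25.8% | 55.0% |
| 2% | 80% | 6.5% | 1.31 | 11.7% | 15.2% | 31.2% |
| 3% | 80% | 7.2% | 1.47 | 19.3% | 26.6% | 56.5% |
| 5% | 80% | 8.6% | 1.78 | 39.5% | 54.6% | 91.0% |

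At a 10% usual-care rate the same inputs give odds ratios of 1.09 to 1.38. Rejection is then 6.1% to 23.6% at 30×50 and 6.6% to 32.9% at 30×333, both at ICC 0.03.

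**The case against.** The strongest reply is that the sentence in Section 6.2 means only that the algorithm runs without a PCP triggering it. That fits the passive web service described in Sections 10.2 and 13.1.4, and it is a fair reading. The sentence is loose rather than false. It still does not establish comparable cohorts, since identical rules applied to inputs that differ by arm need not select the same patients.

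A reader might infer something stronger: because the trial aims to raise diagnosis and MOUD, arm must change the cohort. The documents do not support that. The automatic display is for patients who already have OUD or are at high risk, and H1.1 concerns patients already flagged at an index visit. A diagnosis prompted by an alert leaves that patient's index where it was. Differential entry needs the narrower routes in Step 1, and these may be thin. Manual opening is unprompted, and in the pilot PCPs used the tool in only 5% of eligible high-risk encounters (Section 4.1). Section 10.1 frames index visits as visits with PCPs, which makes an index set by a pharmacist speculative. Training is the most plausible route, but its size is unknown.

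A reader might also infer that more than 10,000 patients would make even a small bias significant. Clustering limits this. At ICC 0.03, going from 50 to 333 patients per clinic raises effective n per arm only from 304 to 456, and the detectable odds ratio at a 5% usual-care rate falls only from about 2.4 to 2.1.

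There is some existing cover. Section 2.5 gives the DSMB index-visit counts and baseline characteristics by blinded arm, Section 13.8 reports baseline by arm, and Section 8.3 logs why each patient was flagged high risk. Section 13.3 defers methodological decisions to a separate Statistical Analysis Plan that is not in the text reviewed and may address the point. None of the supplied text compares entry route by arm.

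**Conclusion.** The concern holds in a limited form: arm can affect who enters and when. The documents do not show that it does, and they give no size. Three of the four primary outcomes (H1.2, H2.1, H2.2) and Aims 3 and 4 are exposed; H1.1 is exposed only through loss of patients diagnosed before being flagged.

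The odds ratios of about 1.2 to 1.8 rest wholly on assumed shares of extra entrants (2% to 5%) and assumed outcome rates among them (50% to 80%), with a 5% usual-care rate and no true effect. At the low end, type I error at ICC 0.03 rises only to about 7.5% to 9%. It becomes serious at the upper end, or if the ICC is near 0.01.

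This does not justify redefining the primary cohort. Requiring a pre-go-live diagnosis or MOUD record for those routes would drop genuine OUD patients new to the system in both arms. It could also select differently by arm: an unflagged patient diagnosed early in an intervention clinic would be excluded, while a usual-care counterpart could be flagged later and kept.

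**What to change.** 1. In Sections 6.1 and 10.1 and in the index-date definition, state that only primary care encounters at which the web service fires automatically in both arms can set an index visit. Manually opened and non-PCP encounters cannot.
2. Keep the present primary cohort. Prespecify a sensitivity analysis of H1.2, H2.1, H2.2 and Aim 3 limited to patients who qualify, by any of the three routes, on data recorded before go-live. Report entry counts and timing by route and arm.
3. In Section 6.2, replace the closing clause of the quoted sentence with wording that the algorithm runs without a PCP trigger but draws on EHR data that clinicians enter.

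Cost: wording, a date filter and one additional table. The sensitivity analysis will have fewer patients. It also needs an EHR lookback to go-live, whereas Section 6.1 plans for the year before index. At HealthPartners, with 18 months of accrual (18 + 3 = 21 if extended), that year does not reach go-live for patients indexed after month 12, so a longer extract is needed for them. The same applies to the last month at Geisinger if its accrual is extended (10 + 3 = 13 months).
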